### 7.2.5. Final Evaluation Visit (Week 36) or Early Discontinuation

The following procedures must be performed and recorded at the Final Evaluation Visit for each subject. Following treatment, subjects will be followed until Week 36, or until the time when severity scores for GL, FHL, and LCL return to baseline (Day 1 pretreatment) or worse, based on both the investigator and subject evaluations (minimum of 24 weeks and up to 36 weeks after treatment), whichever occurs first. Subjects will then have a Final Evaluation Visit at which time the following procedures must be performed:

patient education: discuss the potential effect of DAXI for injection treatment, explain the PFWS, PFHWS, and PLCWS measurement and the categories of the severity assessment scales, and instruct the subjects to consider depth of lines for severity grading. Use the provided Patient Education Brochure.

8. Perform a physical examination

14. Measure and record vital signs (body temperature, respiratory rate, sitting radial pulse, and sitting systolic and diastolic blood pressure).

16. Collect blood and urine samples for clinical safety laboratory tests (hematology, serum chemistry, and urinalysis).

If there are no safety concerns, the subject's participation in the study is complete at this visit.

#### 7.2.6. Variation from Scheduled Visit Days

To allow for scheduling flexibility, limited variation will be permitted from the specified time of each visit ([Table 4](#)).

**Table 4: Allowed Variation from Scheduled Visit Days**

Visit	Allowed Variation
Week 1 Safety Call	+ 2 days
Week 2, Week 4	± 3 days
Weeks 8, 12, 16, 20, 24, 28, 32, and 36	±7 days

#### 7.3. Efficacy Assessments

Investigator assessments should be performed by the same evaluator throughout the study for a given subject. It is recommended that visit assessments be completed as close to the same time of day as possible.

Subject assessments of GL, FHL, and LCL severity (ie, PFWS, PFHWS, and PLCWS) must be completed prior to investigator assessments (ie, IGA-FWS, IGA-FHLS, and IGA-LCWS). In addition, subjects should complete the PNA, P-GAIS, and Satisfaction with Treatment items prior to completing the FASE and FACE-Q assessments. Subjects who wear contact lenses should view the treatment areas while wearing their contact lenses. Subjects who wear glasses must have sufficient visual acuity to view the treatment areas without glasses. Subject assessments of GL, FHL, and LCL severity should be performed at rest first, followed by the assessment at maximum contraction.

The IGA-FWS, IGA-FHWS and IGA-LCWS will be conducted with the subject in a sitting position in a room with good overhead lighting or natural light from a window (but not direct sunlight). To ensure consistent eye positioning during the assessment, the investigator should ask the subject to focus on a fixed point in the examination room. Investigator assessments of GL,

FHL, and LCL severity should be performed at rest first, followed by the assessment at maximum contraction.

Planned timepoints for all efficacy assessments are provided in the SOA ([Section 1.3](#)).

### 7.3.1. Patient Frown Wrinkle Severity (PFWS)

Subjects will assess the visual appearance of GL using the PFWS at rest and at maximum frown. The assessment form will be provided directly to the subject to complete while reviewing their GL treated area using the supplied handheld mirror. The assessment will represent wrinkle severity at the given time point and will not be based on a comparison to the pre-treatment defect level. More detail is provided in [Appendix 2](#).

**Table 5: Patient Frown Wrinkle Severity (PFWS)**

Rating Score	Frown Wrinkle Severity	Description
0	None	No wrinkles
1	Mild	Very shallow wrinkles
2	Moderate	Moderate wrinkles
3	Severe	Deep wrinkles

### 7.3.2. Patient Forehead Wrinkle Severity (PFHWS)

Subjects will assess the visual appearance of FHL using the PFHWS at rest and at maximum eyebrow elevation. The assessment form will be provided directly to the subject to complete while reviewing the FHL areas using the supplied handheld mirror. The assessment will represent wrinkle severity at the given time point and will not be based on a comparison to the pre-treatment defect level. More detail is provided in [Appendix 3](#).

**Table 6: Patient Forehead Wrinkle Severity (PFHWS)**

Rating Score	Forehead Wrinkle Severity	Description	
		At Rest	At Maximum Brow Elevation
0	None	No horizontal forehead lines	None to minimally visible horizontal forehead line(s)
1	Mild	Barely visible, shallow horizontal forehead line(s)	Visible, shallow horizontal forehead line(s)
2	Moderate	Clearly visible, moderate depth horizontal forehead line(s)	Clearly visible, moderate depth horizontal forehead line(s)
3	Severe	Clearly visible, deep horizontal forehead line(s) with redundancy of skin	Clearly visible, deep horizontal forehead line(s) with redundancy of skin

### 7.3.3. Patient Lateral Canthal Wrinkle Severity (PLCWS)

Subjects will assess the visual appearance of LCL using the PLCWS at rest and at maximum smile, to assess the severity of the LCL on each side of the face (a separate score will be assigned for each side). The assessment form will be provided directly to the subject to complete while reviewing his or her LCL using the supplied handheld mirror. The assessment will represent wrinkle severity at the given time point and will not be based on a comparison to the pre-

treatment defect level. Scores at screening and baseline must be consistent bilaterally. More detail is provided in [Appendix 4](#).

**Table 7: Patient Lateral Canthal Wrinkle Severity (PLCWS)**

Rating Score	Lateral Canthal Wrinkle Severity	Description
0	None	No line(s) lateral to the lateral canthus
1	Mild	Barely visible, shallow line(s) lateral to the lateral canthus
2	Moderate	Clearly visible, moderately deep line(s) lateral to the lateral canthus
3	Severe	Clearly visible deep line(s) lateral to the lateral canthus with redundancy of skin

#### 7.3.4. Global Aesthetic Improvement Scale (GAIS)

The investigator and subject will assess the visual appearance (at maximum contraction) of the improvement from the baseline condition in GL, FHL, and LCL (individually) using the following 7-point severity GAIS ([Table 8](#)). Subjects will use the baseline assessment photograph for comparison when reviewing the visual appearance for GL, FHL, and LCL to assess improvement following treatment.

The Patient GAIS assessment form ([Appendix 5](#)) will be provided directly to the subject to complete while reviewing each treatment area (at maximum contraction) using the supplied handheld mirror. These subject assessments must be completed before the investigator completes the IGA assessments and the investigator GAIS.

**Table 8: Global Aesthetic Improvement Scale (GAIS)**

Rating Score	Wrinkle Improvement
-3	Very Much Worse
-2	Much Worse
-1	Worse
0	No Change
1	Improved
2	Much Improved
3	Very Much Improved

#### 7.3.5. Facial Age Self Evaluation (FASE)

Subject will be asked to rate their perceived age on a FASE questionnaire ([Appendix 6](#)). This assessment will be given after the subject's completion of the Patient GAIS, the subject will be given a questionnaire to rate their perception of how old they think they look following the treatment.

#### 7.3.6. Subject Global Satisfaction with Treatment Questionnaires

Subject will provide a rating of their satisfaction with the treatment results. Following the subject's completion of the Patient GAIS, the subject will be given the Subject Global Satisfaction with Treatment Questionnaires to rate their satisfaction with the treatment results.

Subjects will be asked how satisfied or dissatisfied they are with how the treated area of the face looks ([Appendix 7](#)).

### 7.3.7. FACE-Q™

Subject will be asked to complete the FACE-Q™ Appraisal of Lines: Overall, FACE-Q™ Appraisal of Lines: Forehead, FACE-Q™ Appraisal of Lines: Between Eyebrows, FACE-Q™ Appraisal of Lines: Crow's Feet Lines, FACE-Q™ Satisfaction with Forehead and Eyebrows, FACE-Q™ Satisfaction with Outcome and FACE-Q™ Psychological Function. Refer to [Appendix 8](#).

### 7.3.8. Patient Naturalness Assessment (PNA)

The subject will be asked to rate how strongly they agree or disagree with the statement "the results of my treatment look natural." More detail is provided in [Appendix 9](#).

### 7.3.9. Investigator Global Assessment Frown Wrinkle Severity (IGA-FWS)

The investigator will assess the visual appearance of the GL at rest first, and then at maximum frown using the IGA-FWS with the following 4-point scale ([Table 9](#)). More detail is provided in [Appendix 10](#).

**Table 9: Investigator Global Assessment Facial Wrinkle Severity (IGA-FWS)**

Rating Score	Frown Wrinkle Severity	Description
0	None	No wrinkles
1	Mild	Very shallow wrinkles
2	Moderate	Moderate wrinkles
3	Severe	Deep and furrowed wrinkles

The assessment will represent wrinkle severity at the given time point and will not be based on a comparison to the pre-treatment level. Assessments should be completed by the same Revance-approved and trained investigator and conducted as close to the same time of day as possible at each visit. To ensure standardized ratings of wrinkle severity across investigators, a set of training photographs exhibiting the grades of wrinkle severity will be used for training. A photo guide will be provided to each study center to assist in the investigator's assessment.

### 7.3.10. Investigator Global Assessment Forehead Wrinkle Severity (IGA-FHWS)

The investigator will assess the visual appearance of the FHL at rest first and then at maximum eyebrow elevation using the IGA-FHWS with the following 4-point scale ([Table 10](#)). More detail is provided in [Appendix 11](#).

**Table 10: Investigator Global Assessment Forehead Wrinkle Severity (IGA-FHWS)**

Rating Score	Forehead Wrinkle Severity	Description	
		At Rest	At Maximum Brow Elevation
0	None	No horizontal forehead lines	None to minimally visible horizontal forehead line(s)
1	Mild	Barely visible, shallow horizontal forehead line(s)	Visible, shallow horizontal forehead line(s)
2	Moderate	Clearly visible, moderate depth horizontal forehead line(s)	Clearly visible, moderate depth horizontal forehead line(s)
3	Severe	Clearly visible, deep horizontal forehead line(s) with redundancy of skin	Clearly visible, deep horizontal forehead line(s) with redundancy of skin

### 7.3.11. Investigator Global Assessment of Lateral Canthal Wrinkle Severity (IGA-LCWS)

The investigator will assess the visual appearance of the LCL on each side of the face, at rest first and then at maximum smile, using the IGA-LCWS with the following 4-point scale (Table 9). More detail is provided in (Appendix 12).

**Table 11: Investigator Global Assessment Lateral Canthal Wrinkle Severity (IGA-LCWS)**

Rating Score	Lateral Canthal Wrinkle Severity	Description
0	None	None to minimally visible line(s) lateral to the lateral canthus
1	Mild	Visible, shallow line(s) lateral to the lateral canthus
2	Moderate	Clearly visible, moderately deep line(s) lateral to the lateral canthus
3	Severe	Clearly visible, deep line(s) lateral to the lateral canthus with redundancy of skin

The assessment will represent wrinkle severity at the given time point and will not be based on a comparison to the pre-treatment level. Assessments should be completed by the same Revance-approved and trained investigator and conducted as close to the same time of day as possible at each visit. To ensure standardized ratings of wrinkle severity across investigators, a

set of training photographs exhibiting the grades of wrinkle severity will be used for investigator training. A photo guide will be provided to each study center to assist in the investigator's assessment. Scores at screening and baseline must be consistent bilaterally.

## 7.4. Safety Assessments

Planned timepoints for all safety assessments are provided in the SOA (Section 1.3).

### 7.4.1. Adverse Events and Serious Adverse Events

#### 7.4.1.1. Evaluation of Adverse Events and Serious Adverse Events

For this protocol, an **adverse event (AE)** is any untoward medical occurrence (e.g., sign, symptom, disease, syndrome, intercurrent illness, clinically significant abnormal laboratory finding, injury or accident) that emerges or worsens following administration of investigational product and until the end of study participation that may not necessarily have a causal relationship to the administration of the investigational product. An AE can therefore be any unfavorable and/or unintended sign (including a clinically significant abnormal laboratory result), symptom, or disease temporally associated with the use of an investigational product, whether or not considered related to the investigational product. A treatment-emergent AE is one that occurs after any period of exposure to treatment.

Pre-existing conditions, which increase in frequency or severity or a change in nature as a consequence of an investigational product use will also be considered an adverse event.

An unexpected AE is an adverse reaction, the nature or severity of which is not consistent with the applicable product information (e.g., Investigator's Brochure for an unapproved investigational product or package insert/summary of product characteristics for an approved product).

Any change in the study safety evaluations, (e.g., vital signs, injection site evaluation) post-treatment determined to be clinically significant by the investigator must be reported as an AE.

An **SAE** is any untoward medical occurrence that results in any of the following outcomes:

- Death

- Life-threatening, (i.e., the subject was, in the opinion of the Investigator, at immediate risk of death from the event as it occurred. It does not apply to an AE that hypothetically might have caused death if it were more severe)
- Persistent or significant disability/incapacity or substantial disruption of the subject's ability to carry out normal life functions
- Requires in-patient hospitalization or prolongs hospitalization (i.e., a prolonged hospitalization beyond the expected length of stay; hospitalizations for elective medical/surgical procedures, scheduled treatments, or routine check-ups are not SAEs by this criterion)
- Congenital anomaly/birth defect (i.e., an adverse outcome in a child or fetus of a subject exposed to the molecule or investigational product before conception or during pregnancy)
- Does not meet any of the above serious criteria but based upon appropriate medical judgement may jeopardize the subject or may require medical or surgical intervention to prevent one of the outcomes listed above (i.e., is a significant or important medical event)

#### **7.4.1.2. Assessment and Reporting Requirements**

The investigator will assess each subject post-treatment and at each subsequent study visit for the occurrence of AEs. In order to avoid bias in eliciting AEs, subjects should be asked the following non-leading question: "How have you felt since your last visit?" All AEs (serious and non-serious) will be collected from the signing of the ICF until the Final Evaluation Visit. Any AE reported by the subject must be recorded on the source documents and eCRFs.

All AEs will be collected after IP administration until Week 36 or the Final Evaluation Visit at all timepoints as specified in the SOA ([Section 1.3](#)). Medical occurrences related to protocol-mandated intervention that begin before the start of study intervention but after obtaining informed consent will be recorded as AEs.

[figure not shown]
All SAEs will be recorded and reported to Revance or designee immediately within 24 hours of their awareness of the event. All fatal or life-threatening SAEs should be telephoned to Revance or the designee's authorized representative as soon as the investigator learns of the event.

[figure not shown]

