#### **8.3.2. Safety Analyses**

Adverse events (AEs) occurring during the study will be recorded and classified according to MedDRA terminology. Those occurred one or after treatment are considered as treatment emergent. All reported TEAEs will be summarized, in terms of the number of subjects reporting events, system organ class, preferred term, severity, relationship to study drug, outcome, action taken and seriousness. For summarization of event causality and seriousness, subjects will be counted only once within a system organ class or preferred term using the event with the event with the greatest relationship for causality and the event with the highest severity. A summary of TEAEs leading to discontinuation will also be provided.

A by-subject listing of any SAEs will be provided and all SAEs will be summarized by severity and relationship to study treatment.

Clinical laboratory test and vital sign results will be summarized by visit and if applicable a shift table will be used to evaluate the shift in status from baseline at each visit. [REDACTED]

[REDACTED] Physical examination, injection site findings, [REDACTED] will be summarized as described in the SAP.

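### The protocol gives two conflicting starts for adverse event collection, an AE definition that fits neither before dosing, and a causality phrase on worsening that sites could read as a restriction

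*Protocol*

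**What the plan says.** Section 7.4.1.2 gives two starts for collection. The first is consent: "All AEs (serious and non-serious) will be collected from the signing of the ICF until the Final Evaluation Visit". The next paragraph gives the other: "All AEs will be collected after IP administration until Week 36 or the Final Evaluation Visit at all timepoints as specified in the SOA". It then adds a pre-dose provision: "Medical occurrences related to protocol-mandated intervention that begin before the start of study intervention but after obtaining informed consent will be recorded as AEs".

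Section 7.4.1.1 defines an AE for this protocol as an untoward occurrence "that emerges or worsens following administration of investigational product and until the end of study participation", and says that it "may not necessarily have a causal relationship to the administration of the investigational product". A later sentence in the same section takes up disorders that were already there. Without its opening and its last word it reads: "which increase in frequency or severity or a change in nature as a consequence of an investigational product use will also be considered an adverse".

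Treatment emergence is described twice. Section 7.4.1.1 ties it to occurrence after exposure to treatment. Section 8.3.2 says: "Those occurred one or after treatment are considered as treatment emergent" (presumably meaning on or after treatment). Neither sentence mentions worsening.

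**The concern.** These are instructions to sites about what to write on the AE form. If they conflict, sites will record different things, and no analysis rule applied later can recover an event or a worsening that was never entered.

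Safety is part of the primary objective, the study is single-arm, and TEAE incidence, severity and relationship are among its listed safety evaluations. With up to 8 sites and no comparator, a difference in recording practice has no control group in which it would also appear.

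Two things are at stake: whether an event between consent and injection is an AE at all, and whether a condition already present at injection that later worsens is recorded and counted in the same way everywhere.

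**Working it through.** No figure in the protocol depends on these rules, so there is nothing to reproduce. The check sets the texts side by side and applies each to the kinds of event that can arise.

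**Rules**

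- Rule A (7.4.1.2, first paragraph): all AEs from consent.
- Rule B (7.4.1.2, second paragraph): all AEs after injection, plus pre-dose occurrences related to a protocol-mandated intervention. The two sentences of this paragraph fit together as one rule with an exception. If Rule A governed, the exception would not be needed.
- Definition D (7.4.1.1): an AE emerges or worsens after dosing, with no causal link required.
- Clause P (7.4.1.1): worsening of a pre-existing condition as a consequence of the product is also an AE.
- TEAE sentences (7.4.1.1 and 8.3.2): occurrence after exposure, or on or after treatment.

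**Applied to four event types**

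| Event | Rule A | Rule B | Definition D | TEAE? |
|---|---|---|---|---|
| (a) Before dosing, unrelated to procedures | AE | not an AE | not an AE | no |
| (b) Before dosing, related to a protocol procedure | AE | AE | not an AE | no |
| (c) New onset after dosing | AE | AE | AE | yes |
| (d) Present before dosing, worsens after it, not attributed to product | AE | AE | AE, unless Clause P is read as the governing rule | not settled |

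**Reading the table**

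1. Rows (a) and (b) show the start conflict. Rules A and B disagree on (a). Definition D excludes both, so the pre-dose provisions of A and B have nothing to collect if the definition is taken literally. The window is the screening period, at most 14 days (7.2.1).
2. Rows (a) to (c) show that the start conflict alone does not change TEAE counts: purely pre-dose events are not TEAEs and new post-dose events always are. One narrow edge is an event on Day 1 before injection, if the garbled sentence in 8.3.2 is read by calendar day.
3. Row (d) is where TEAE status can differ. Suppose a headache starts in screening and worsens on Day 3. A site using Rule A may hold it as one AE with pre-dose onset, which the occurrence-only TEAE sentences can exclude. A site using Rule B may hold it as medical history and enter the worsening as a new post-dose AE, which is a TEAE. A site that treats Clause P as the specific rule may not record an unrelated worsening.
4. Elsewhere the protocol attaches no causality condition to worsening: section 7.4.3 records clinically significant worsening of vital signs as an AE whatever the cause.

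**Scale.** With the planned 48 subjects, one subject classified differently moves TEAE incidence by 1/48 = 0.0208, or 2.1 percentage points. The documents give no basis for estimating how many subjects would be affected.

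**The case against.** The strongest reply is that the harm is small and the wording can be read sensibly.

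- *Worsening.* The word "also" is part of the pre-existing-condition sentence, so it adds cases and does not restrict the definition. The general definition already covers any post-dose worsening, and 7.4.1.7 provides an unrelated category. This stands. A reader might infer that unrelated worsening is not an AE under this protocol, or that incidence is biased downward. The text does not say so; both follow only if a site reads the clause restrictively. Because the clause adds nothing when read correctly, that misreading is a real possibility.
- *Serious events.* A reader might infer that a serious event in screening, unrelated to any procedure, is unreportable under the second paragraph of 7.4.1.2. The SAE definition in 7.4.1.1 has no post-dose limit, and 7.4.1.2 separately requires all SAEs to be reported within 24 hours. The stronger inference fails, although the start of SAE recording should be stated along with that of AEs.
- *TEAE flagging.* How worsening is flagged is often left to the SAP, and section 8.3 calls itself a summary. That is fair for 8.3.2 taken alone. It does not answer the recording conflict in 7.4.1.1 and 7.4.1.2, which an SAP cannot repair.
- *Hidden material.* The schedule of assessments is not visible. The visible sentences conflict on their own, so this does not remove the point, but it limits what can be said about actual site practice.

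**Conclusion.** The concern holds as an internal contradiction in the recording rules. There are two competing collection starts and an AE definition that matches neither before dosing. The causality phrase on pre-existing conditions is a redundancy open to a restrictive reading, not a strict contradiction.

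A reader might conclude that the same event is a TEAE at one site and not at another as a general matter. The documents do not support that. A difference is possible only for a condition present before dosing that worsens afterwards, because both TEAE sentences speak only of occurrence. Even there it depends on how each site reads the rules.

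The 2.1 points per subject assumes 48 treated subjects and describes one reclassification, not an expected effect. The change is worth making because it is cheap and has to reach sites before data are recorded.

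**What to change.** 1. In 7.4.1.2, reconcile the two paragraphs to a single start of AE and SAE recording and delete the competing sentence. Align the AE definition in 7.4.1.1 with the start chosen; otherwise a consent start would still collect events that the definition excludes.
2. In 7.4.1.1, remove the phrase tying worsening of a pre-existing condition to use of the product, so that post-dose worsening is recorded regardless of causality and relationship is judged afterwards.
3. Use one TEAE definition in 7.4.1.1 and 8.3.2, covering onset or worsening on or after the first injection, and correct the garbled sentence in 8.3.2.

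The cost is a few sentences in three sections and a matching line in the eCRF completion instructions. The reported AE and TEAE rates may come out slightly higher, because worsening that some sites might have left out will be recorded.
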